5.7.1 Highly Effective Methods of Contraception

- Male condoms with spermicide
- Hormonal methods of contraception including combined oral contraceptive pills, vaginal ring, injectables, implants and intrauterine devices (IUDs) such as Mirena® by WOCBP subject or male subject's WOCBP partner. Female partners of male subjects participating in the study may use hormone based contraceptives as one of the acceptable methods of contraception since they will not be receiving study drug
- Nonhormonal IUDs, such as ParaGard®
- Tubal ligation
- Vasectomy
- Complete Abstinence: Complete abstinence is defined as complete avoidance of heterosexual intercourse and is an acceptable form of contraception for all study drugs. Subjects who choose complete abstinence are not required to use a second method of contraception. Acceptable alternate methods of highly effective contraception must be discussed in the event that the subject chooses to forego complete abstinence.

5.7.2 Less Effective Methods of Contraception

- Diaphragm with spermicide
- Cervical cap with spermicide
- Vaginal sponge
- Male Condom* without spermicide
- Progestin only pills by WOCBP subject or male subject's WOCBP partner
- Female Condom*.

* A male and female condom must not be used together

5.8 Use in Pregnancy

If a subject becomes pregnant while on treatment, the subject will immediately be removed from the study. The site will contact the subject at least monthly and document the subject's status until the pregnancy has been completed or terminated. The outcome of the pregnancy will be reported to HCRN **within 24 hours** of discovery of event and HCRN will notify the sponsor-investigator, Bristol-Myers Squibb (BMS) and Syndax **within 24 hours** if the outcome is a serious adverse experience (e.g., death, abortion, congenital anomaly, or other disabling or life-threatening complication to the mother or newborn). The site investigator will make every effort to obtain permission to follow the outcome of the pregnancy and report the condition of the fetus or newborn to HCRN who will report to BMS and Syndax. If a male subject impregnates his female partner the study personnel at the site must be informed immediately and the pregnancy reported to HCRN who will report the event to BMS and Syndax and follow as described above.

6. TOXICITIES AND DOSE DELAYS/DOSE MODIFICATIONS

The NCI Common Terminology Criteria for Adverse Events (CTCAE) version 4 will be used to grade AEs.

Subjects enrolled in this study will be evaluated clinically and with standard laboratory tests before and at regular intervals during their participation in this study as specified in Study Calendar & Evaluations.

Subjects will be evaluated for AEs (all grades), SAEs, and AEs requiring study drug interruption or discontinuation as specified in Study Calendar & Evaluations.

6.1 Dose Delays/Dose Modifications

All dose modifications should be based on the AE requiring the greatest modification and should be properly documented in source documents. Investigators may take a more conservative approach than the guidelines outlined below based on clinical judgment that is in the best interest of the subject. **NOTE:** if one or more study drugs are permanently discontinued, subjects may continue with the remaining drugs per protocol at the discretion of the treating physician if the subject is receiving clinical benefit.

For subjects with immune-related adverse events (irAEs), if the management guidelines suggest delay or discontinuation, both nivolumab and ipilimumab should be held or discontinued. In the event that ipilimumab must be permanently discontinued due to an AE which can be directly attributed to ipilimumab (e.g. an infusion reaction), nivolumab may be continued per protocol at the discretion of the treating physician.

6.1.1 Entinostat

The dose levels used for dose modifications of entinostat will be 5, 3 or 2 mg PO QW, with the chosen dose based on the starting dose. If a dose below 2mg PO QW is required for entinostat, entinostat must be permanently discontinued, and the subject followed-up per protocol. If a dose of entinostat is held for toxicity and cannot be resumed within 48 hours, the dose will not be made up, and the subject will continue to follow the standard dosing schedule. If the dose of entinostat is held for toxicity and can be resumed within 48 hours, the dose will be given, and the subject will continue to follow the standard dosing schedule (i.e., the next dose will be given on time).

Management of toxicities that are at least possibly related to entinostat will be managed as follows:

Non-hematologic Toxicity	
Toxicity	Entinostat Dose Modifications
Grade 4	Administer symptomatic remedies/start prophylaxis. Permanently discontinue drug
Grade 3	
Administer symptomatic remedies/ start prophylaxis. Hold dose until recovery to Grade 1 or baseline under the following directions:
 
 1. If recovered within 1 week, resume study drug at prior dose. If not recovered within 1 week, continue to hold dose. 2. If recovered within 2-4 weeks, resume study drug as follows: 
 a. If receiving 5 mg, restart study drug at 3 mg b. If receiving 3 mg, restart study drug at 2 mg c. If receiving 2 mg, permanently discontinue study drug 
If not recovered within 4 weeks, permanently discontinue study drug.

Recurrence of the same \geq Grade 3 toxicity despite dose reduction	
If the same \geqGrade 3 event recurs:
 
 1. Administer symptomatic remedies/ start prophylaxis. Hold¹ dose until recovery to Grade 1 or baseline. 2. If recovered within 2 weeks, resume study drug as follows: 
 a. If receiving 5 mg, restart study drug at 3 mg b. If receiving 3 mg, restart study drug at 2 mg c. If receiving 2 mg, permanently discontinue study drug 3. If the same \geqGrade 3 event recurs (i.e., third occurrence) despite entinostat dose reduction to 2 mg, as described above, permanently discontinue study drug.
\leq Grade 2	
Administer symptomatic remedies / start prophylaxis.
 
Dosing of study drug may be interrupted (held)¹ at the Investigator's discretion.
 
 1. If dose is held for 4 consecutive weeks, permanently discontinue study drug. 2. If toxicity resolves, resume entinostat at the original dose.

¹If greater than 50% of doses are missed during any 6 week period, discontinue from study drug treatment.

Hematologic Toxicity	
Toxicity	Entinostat Dose Modifications
≥Grade 3 neutropenia, ≥Grade 3 febrile neutropenia, ≥Grade 3 uncomplicated thrombocytopenia, or Grade 2 complicated thrombocytopenia	
Administer symptomatic remedies/start prophylaxis. Hold dose¹ until recovery to Grade 1 or study baseline under the following direction:
 
 1. If not recovered by next scheduled dose, skip the dose. If recovered by next scheduled dose, resume study drug at prior dose. 2. If receiving 2 mg dose, and not recovered by either of the next 2 scheduled doses, permanently discontinue study treatment. Otherwise, skip each dose. If recovered for either of these doses, resume study drug as follows: 
 a. If receiving 5 mg, restart study drug at 3 mg. b. If receiving 3 mg, restart study drug at 2 mg. 3. If not recovered within 4 weeks, permanently discontinue study drug.
Recurrence of the same hematologic toxicity	
If the same hematologic toxicity recurs:
 
 1. Administer symptomatic remedies/ start prophylaxis. Hold¹ dose until recovery to Grade 1 or baseline. 2. If recovered within 2 weeks, resume study drug as follows: 
 a. If receiving 5 mg, restart study drug at 3 mg b. If receiving 3 mg, restart study drug at 2 mg c. If receiving 2 mg, permanently discontinue study drug 3. If the same ≥ Grade 3 event recurs (i.e., third occurrence) despite entinostat dose reduction to 2 mg, as described above, permanently discontinue study drug.

¹If greater than 50% of doses are missed during any 6 week period, discontinue from study drug treatment.

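### Non-hematologic entinostat table: a Grade 3 toxicity that returns at Grade 4 in a subject reduced from 5 mg to 3 mg meets one row that stops the drug and another that restarts it at 2 mg after recovery within 2 weeks

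*Combined protocol and SAP*

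**What the plan says.** The table in Section 6.1.1 applies to toxicities at least possibly related to entinostat. Four parts of it matter here.

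- **Grade 4 row:** "Administer symptomatic remedies/start prophylaxis. Permanently discontinue drug". It makes no distinction by occurrence or dose level.
- **Grade 3 row:** hold until Grade 1 or baseline. "If recovered within 1 week, resume study drug at prior dose". Recovery in 2 to 4 weeks leads to a restart one level lower (5 to 3 mg, or 3 to 2 mg), or to a stop at 2 mg.
- **Recurrence row:** after a greater-than-or-equal sign, the label reads "Grade 3 toxicity despite dose reduction". The row holds the drug until Grade 1 or baseline, then "If recovered within 2 weeks, resume study drug as follows". At 5 mg the restart is at 3 mg. For the next level, "If receiving 3 mg, restart study drug at 2 mg". At 2 mg the drug stops. A further step stops it on a third occurrence at 2 mg.
- **Footnote on the recurrence row's hold:** a subject who misses more than half of the doses in any 6-week period comes off study drug.

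Section 6.1 sets two general rules above the table: "All dose modifications should be based on the AE requiring the greatest modification", and "Investigators may take a more conservative approach than the guidelines outlined below", on clinical judgment in the subject's interest.

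**The concern.** The Grade 4 row and the recurrence row overlap, and neither refers to the other. Where both apply, one ends entinostat for good and the other allows it to be given again. A site that follows the recurrence row could re-expose a subject to entinostat after a Grade 4 non-hematologic toxicity. Two sites could also handle the same event differently, each departing from one row.

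The table is still in use. Accrual halts after the safety lead-in, but subjects on treatment continue (Sections 5.3 and 12.3).

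**Working it through.** No sample size, power or error rate enters this point, and the plan states no figure to reproduce. The check traces the rows for one subject and then counts the states in which they disagree.

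**Step 1. One subject.** A subject on 5 mg has a related Grade 3 event that recovers in 2 to 4 weeks, and restarts at 3 mg under the Grade 3 row. The same event returns at Grade 4 and recovers to Grade 1 within 2 weeks. The Grade 4 row gives a permanent stop. The recurrence row gives a restart at 2 mg. Both conditions are met. If recovery takes longer than 2 weeks, the recurrence row offers no restart, so the conflict does not arise.

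**Step 2. Does the greater-than-or-equal sign matter?** A first Grade 4 event already ends entinostat, so only a first Grade 3 event can lead to a recurrence. The sign, used three times in the row, therefore has an effect on dosing only when the event returns at Grade 4. Either it is surplus or it brings Grade 4 into a hold-and-restart row.

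**Step 3. The footnote.** Dosing is weekly, so 6 weeks hold 6 doses, and more than 50% means at least 4 missed.

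- Recurrence hold alone, resolved in 2 weeks: about 2 missed, 2/6 = 33%. Even 3/6 = 50% does not exceed the limit.
- Earlier hold in the same 6 weeks, for example 2 + 2 = 4 missed: 4/6 = 67%. The footnote stops the drug, and the outcome agrees with the Grade 4 row.

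The footnote removes the conflict when the two holds are close together, but not when the recurrence comes later.

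**Step 4. All starting and current doses, for a Grade 4 recurrence that recovers within 2 weeks.**

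| Started | Now | Grade 4 row | Recurrence row | Conflict | Row label fits |
|---|---|---|---|---|---|
| 5 mg | 5 mg | stop | restart at 3 mg | yes | no |
| 5 mg | 3 mg | stop | restart at 2 mg | yes | yes |
| 5 mg | 2 mg | stop | stop | no | yes |
| 3 mg | 3 mg | stop | restart at 2 mg | yes | no |
| 3 mg | 2 mg | stop | stop | no | yes |
| 2 mg | 2 mg | stop | stop | no | no |

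With the label applied, 1 of 6 states conflicts. On the row's steps alone, 3 of 6 do.

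**Step 5. Ceiling on subjects.** Section 5.2 allows up to 6 subjects at each of 3 levels, so 3 × 6 = 18. With the label applied, only subjects started at 5 mg can be affected: at most 6. On the steps alone, those started at 5 or 3 mg can be: at most 6 + 6 = 12.

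**The case against.** The best defence is that the plan already points to stopping. The Grade 4 row is unqualified. If the recurrence row is read as covering a toxicity that returns at Grade 3, every row can stand. The greatest-modification rule in Section 6.1 leans the same way, and many investigators would apply it so. A site that restarted would have to pass over an explicit stop instruction.

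Most of this stands as evidence of intent, but it does not settle the wording. The greatest-modification rule chooses between adverse events, not between two rows for one event. The more conservative course is permitted, not required. The step that stops the drug at a third occurrence of Grade 3 or higher on 2 mg implies that an earlier recurrence at that threshold need not stop it.

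Three stronger readings are tempting, and the documents do not support them.

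- A reader might infer that the recurrence row restarts entinostat after any Grade 4 recurrence. It does so only with recovery within 2 weeks, only at 5 or 3 mg, and subject to the missed-dose footnote.
- A reader might take the nivolumab table in Section 6.1.3 as the same conflict resolved, since its recurrence line is limited to Grade 3 and Grade 4 has its own line. Both lines stop nivolumab, so they could not conflict whatever grades they covered.
- A reader might suppose that the wording came from the hematologic table, whose row headed "Recurrence of the same hematologic toxicity" has nearly identical steps. The documents say nothing of drafting history. That table has no Grade 4 stop row, so it has no such conflict.

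**Conclusion.** The point holds as a wording conflict with a small patient-safety consequence. For a Grade 3 non-hematologic toxicity that returns at Grade 4 in a subject reduced from 5 mg to 3 mg, and recovers within 2 weeks without breaching the missed-dose footnote, the table gives incompatible instructions, and Section 6.1 does not formally choose between them.

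The size is small. The sequence needs a related Grade 3 event, slow recovery, a dose reduction, a Grade 4 return and quick recovery. The documents give no rate for it, so no expected number can be stated; it is probably rare. The ceiling of 6 subjects rests on the limit in Section 5.2; the synopsis speaks of a minimum of 6 at the first level. If 5 mg cleared the lead-in, all lead-in subjects would have started at that dose.

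A reader might extend the conflict to subjects not yet reduced, who can reach a recurrence after resuming at the prior dose. The row's 5 mg step suggests that they were in mind, since nobody can be on 5 mg after a reduction. The label does not fit them, however, so that extension remains uncertain.

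Nothing here touches the objective response rate analysis or the Simon design figures.

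**What to change.** In the non-hematologic recurrence row, delete the greater-than-or-equal sign before Grade 3 in all three places. Add one sentence: any Grade 4 non-hematologic event at least possibly related to entinostat, whether first or recurrent, permanently discontinues entinostat. This removes the conflict in every dose state, including the uncertain ones. It does not cure the mismatch between the row's label and its 5 mg step, which the same edit could clarify.

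The cost is one table row in a short amendment for subjects still on treatment. The few subjects affected, if any, lose a lower-dose re-challenge, which the Grade 4 row already forbids.

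### Entinostat non-hematologic table: the recurrence row's heading contradicts its own 5 mg step, so a short repeat Grade 3 event at 5 mg can mean either 5 mg or 3 mg

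*Combined protocol and SAP*

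**What the plan says.** Section 6.1.1 sets three entinostat levels for dose modification: 5, 3 and 2 mg weekly. Section 5.2 starts the lead-in at 5 mg, its highest level. Three rows of the non-hematologic table matter here.

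- **Grade 4 row:** "Permanently discontinue drug".
- **Grade 3 row:** hold, then "If recovered within 1 week, resume study drug at prior dose". Recovery in 2 to 4 weeks means one level down, or stopping at 2 mg. The row ends "If not recovered within 4 weeks, permanently discontinue study drug". Nothing confines it to a first event.
- **Recurrence row:** its heading covers recurrent "Grade 3 toxicity despite dose reduction", with a greater-than-or-equal sign before the grade. Its body is triggered whenever the same event of Grade 3 or above recurs. It continues "If recovered within 2 weeks, resume study drug as follows", and step 2a is "If receiving 5 mg, restart study drug at 3 mg". Steps 2b and 2c go from 3 to 2 mg and stop at 2 mg. Step 3 covers the case where the same "event recurs (i.e., third occurrence) despite entinostat dose reduction to 2 mg, as described above, permanently discontinue study drug".

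The hematologic table in the same section uses the same step 2 branches, but its recurrence row is headed simply "Recurrence of the same hematologic toxicity".

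**The concern.** A patient whose first Grade 3 event cleared within a week went back to the same dose, so no reduction was made for it. If that event returns and again clears within a week, two rows claim the patient. The Grade 3 row keeps the dose. The recurrence row's heading appears to exclude the patient, but its body, and step 2a in particular, lowers the dose.

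This is a safety dosing rule still in use. Sections 5 and 5.3 halt accrual after the lead-in but keep treated patients on therapy. Two sites could give different doses after the same event, and both could claim to follow the protocol. Under the Grade 3 row alone, short repeat Grade 3 events would never require a reduction.

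A second clash sits in the same row. Because it covers Grade 3 and above, an event that recurs at Grade 4 has a restart path there, while the Grade 4 row ends treatment.

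**Working it through.** The plan states no figure on this point, so the check sets the rows side by side and follows patients through them.

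**Inputs.** Dose levels and row actions: Section 6.1.1. Starting dose and cohort size (up to 6 per level): Section 5.2. Weekly doses per cycle: Sections 5.1.1 (3 per 21 days) and 5.1.2 (4 per 28 days).

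**Step 1: can the heading and step 2a both hold?** The heading requires an earlier reduction. Step 2a addresses a patient on 5 mg, the top level. The table has no clear re-escalation rule, so such a patient has not been reduced. Step 2a can therefore never apply under its own heading.

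**Step 2: same Grade 3 event recurs, no earlier reduction for it, recovery within 1 week.** Recovery within 2 weeks includes recovery within 1 week, so the body of the recurrence row is met.

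| Current dose | Grade 3 row | Recurrence row, body | Difference |
|---|---|---|---|
| 5 mg | 5 mg | 3 mg | (5 − 3)/5 = 40% lower |
| 3 mg | 3 mg | 2 mg | (3 − 2)/3 = 33% lower |
| 2 mg | 2 mg | stop | drug ended |

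At 5 mg the row's own step addresses an unreduced patient. At 3 and 2 mg nothing in the steps contradicts the heading, so the split there depends on giving the body priority. Those cases also need a lower starting cohort (opened after more than 1 DLT at the dose above) or an earlier reduction for a different toxicity.

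**Step 3: exposure from 5 mg.**
- 21-day cycle: 3 × 5 = 15 mg against 3 × 3 = 9 mg.
- 28-day cycle: 4 × 5 = 20 mg against 4 × 3 = 12 mg.

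**Step 4: dose after occurrences 1 to 4, each clearing within a week, from 5 mg.**
- Grade 3 row: 5, 5, 5, 5 mg.
- Recurrence row body: 5, 3, 2 mg, stop.

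**Step 5: where there is no conflict.** If the first event took 2 to 4 weeks to clear, it already led to a reduction, and the path from 5 mg is 3, 2, stop. If the recurrence itself clears at 2 weeks, both rows step down.

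**Step 6: does other text settle it?**
- Section 6.1 tells sites to follow the adverse event calling for the largest change. That chooses between events, not between two rows for one event.
- Section 6.1 lets investigators be more cautious than the table. That permits 3 mg but leaves the required minimum open.
- The missed-dose footnote stops the drug when more than half the doses in 6 weeks are missed. Taking at most one weekly dose lost per short event, two events give 2/6 = 33% and three give 3/6 = 50%, which is not more than half. Only four (4/6 = 67%) would trigger it.

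**The case against.** The best defense is that a row heading defines who is in the row. On that view an unreduced patient stays in the Grade 3 row, the trigger in the body is read within the heading, and step 2a is leftover wording from a list used several times in the section. This is coherent, and at 3 and 2 mg nothing on the page defeats it. At 5 mg it works only by treating an explicit dosing instruction as dead text. A site treating a patient on 5 mg has no reason to do so, particularly when the hematologic table has the same branches under an unrestricted heading.

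A second defense is that the row for Grade 2 or lower mentions resuming at the original dose, which might be read as re-escalation and so return a reduced patient to 5 mg. The more natural meaning is the dose before that hold.

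The objections on size stand. The patient must have the same Grade 3 event twice, each clearing within a week. In the first 6 weeks Section 5.2.1 already counts most attributable Grade 3 non-hematologic events as DLTs. The row conflict there concerns mainly the exempt events, such as brief Grade 3 fatigue, although neither Section 5.2.1 nor Section 6.2 says that a DLT ends entinostat. Investigators may always step down, and Section 6.2 lets the physician change therapy.

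**Conclusion.** The inconsistency is real and is clear at 5 mg: the heading and step 2a cannot both be right, and a short repeat Grade 3 event leads to 5 mg or 3 mg depending on the row used. The Grade 4 clash is a separate, smaller defect in the same row. Priority is low to moderate.

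Four stronger readings are tempting but unsupported.

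- **An equal conflict at all three levels.** At 3 and 2 mg it exists only if the body overrides the heading.
- **The third-occurrence wording in step 3 shows that a step-down at every recurrence was meant.** From 5 mg with a short first event, the body stops the drug at the fourth occurrence. Step 3 fits a 5 mg starter only when the first event already led to a reduction. The likely intent rests instead on step 2a and the parallel hematologic row.
- **A known frequency.** Section 10.1.4 reports multiple short fatigue episodes in some patients, but for Grade 2 or greater. It gives no rate of short recurrent Grade 3 events, so the number affected cannot be computed.
- **An effect on the trial's conclusions.** The RP2D rule and the definition and analysis of ORR are unchanged.

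The conclusion assumes that 5 mg cannot be reached again after a reduction.

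**What to change.** Amend two rows of the non-hematologic table.

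1. Label the Grade 3 row as first occurrence.
2. Retitle the recurrence row *Recurrence of the same Grade 3 toxicity*. Remove the dose-reduction condition, and replace Grade 3 or above with Grade 3 throughout the row, so that Grade 4 always means discontinuation.
3. Reword step 3 to say that if the same Grade 3 event recurs at 2 mg, entinostat stops for good. Delete the third-occurrence parenthesis. Otherwise a patient who started at 5 mg could be on 3 mg at the third occurrence, where step 2b gives 2 mg while the parenthesis ties that occurrence to stopping.
4. Edit 1 removes the Grade 3 row's cover for recurrences that take longer than 2 weeks to clear. Either carry over that row's 2-to-4-week step-down and 4-week stop, or adopt the stricter rule of discontinuing if recovery takes more than 2 weeks. State which applies.

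The cost is a wording amendment, IRB notification under Section 15.1 and a notice to sites, with no new visits, data or patients. Clinically, a few patients would have slightly lower entinostat exposure or stop earlier, and a Grade 4 recurrence would have no restart. If the 2-to-4-week step-down is carried over, it allows a restart that a strict reading of the present recurrence row does not give.
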